#### Eligibility Criteria

## 2. ReActiv8 Therapy

### 2.1. Summary of ReActiv8

ReActiv8 is an implantable electrical stimulation system consisting of the following components:

- 1. Implantable Pulse Generator (IPG) (pre-loaded with IPG Firmware Code and packaged with a Torque Wrench to aid in implant procedure)
- 2. Percutaneous Leads (with Stylet and Suture Sleeves)
- 3. Application Software
- 4. Programmer Wand
- 5. Activator (pre-loaded with Activator Firmware Code)
- 6. Magnet
- 7. Tunneler

The ReActiv8 Programmer Wand and Application Software are provided with a commercially available laptop computer and AC adapter. Commercially available surgical tools such as a 7Fr Introducer Kit is used at implant and is not part of ReActiv8.

ReActiv8 delivers stimulation via electrodes placed adjacent to the medial branch of the dorsal ramus nerve at the preferred location as it crosses the L3 transverse process. The electrodes are located at the distal end of a Stimulation Lead that is connected to an implantable pulse generator (IPG) placed in a surgical pocket typically above the buttocks (in a place similar to that used in Spinal Cord Stimulation implants). Two leads are placed (one each left and right side) and connected to the IPG. The IPG is externally programmable via Application Software stored on a laptop computer. Stimulation is manually initiated by an external device (Activator) and can be stopped with the Activator or Magnet.

The leads incorporate a fixation mechanism that consists of two sets of 3-point tines – one set facing forward and one set facing backwards. The tines are positioned to lie on either side of the intertransversarii lateralis, thus reducing the risk of lead migration by either advancement or retraction. The lead body is a polyurethane tube containing the lead conductor, incorporating a lumen to allow passage of a stylet. Refer to the Implant and Programming Manual (990070-001) for more detail on device specifications and operation.

#### 2.1.1. Implantable Components of ReActiv8

The ReActiv8 IPG, and the two sizes of leads (45 cm and 65 cm) are designed for permanent implant. The implantable components of ReActiv8 are supplied sterile and are intended for single use only.

- Model 5100 ReActv8 Implantable Pulse Generator
- Model 8145 ReActiv8 Percutaneous Lead, 45 cm length
- Model 8165 ReActiv8 Percutaneous Lead, 65 cm length

#### 2.1.2. Non-Implantable Components of ReActiv8

The Torque Wrench and Stylet are provided to facilitate implantation of the IPG and leads. The Application Software and Programmer Wand are used with a laptop computer to communicate with the IPG in order to program the IPG operational mode and settings, read history data from the IPG, and obtain IPG and lead status information. The Activator is used to initiate and/or suspend stimulation. The Magnet is used to enter Magnet Mode (with Magnet Mode operation determined by the programmed parameters of the IPG).

The non-implantable components of the ReActiv8 system are:

- Model 7000 ReActiv8 Activator
- Model 4000 ReActiv8 Magnet
- Model 5500 ReActiv8 Torque Wrench
- Version 1.0.1.6 (English) and 1.0.1.9 (Multilanguage) Application Software
- Model 6000 Programmer Wand
- Model TUN1 Tunneler

The ReActiv8 Programmer Wand and Application Software are provided with a commercially available laptop computer and AC adapter.

### 2.2. Indications for Use

The ReActiv8 System is indicated for bilateral stimulation of the L2 medial branch of the dorsal ramus as it crosses the transverse process at L3 as an aid in the management of intractable chronic low back pain associated with multifidus muscle dysfunction, as evidenced by imaging or physiological testing in adults who have failed therapy including pain medications and physical therapy and are not candidates for spine surgery.

### 2.3. Surgical Implantation and Device Activation

The surgical implantation procedure, device programming, and use by the patient are per the Implant and Programming Manual (990070-001) and the User Manual (990071-001).

### 2.4. Physician and Health Care Personnel Training

All physicians who will implant any portion of the ReActiv8 system must have participated in product training.

## 3. Study Design

The ReActiv8 Stimulation Therapy vs Optimal Medical Management: A Randomized Evaluation (RESTORE) study is a prospective, randomized study comparing ReActiv8 therapy to Optimal Medical Management (OMM). Patients meeting all eligibility criteria will be randomized to either the Treatment group (ReActiv8) or the Control group (OMM). Randomization will be performed according to a random permuted block design stratified by clinical site with a 1:1 allocation ratio.

The primary endpoint will be a comparison of the change in Oswestry Disability Index (ODI) at 1 year between the Treatment and Control groups. After 1-year visit, all patients in the Control group may elect to receive a ReActiv8 device and will continue to be followed through the 2-year visit. Patients in the Control group who do not receive a device after the 1-year visit will be exited from the study at that time.

A minimum of 204 evaluable patients is required to sufficiently power the primary endpoint. To allow for attrition, approximately 230 patients will be randomized at up to 30 clinical sites. To account for screen failures prior to randomization approximately 400 patients may be enrolled.

The study visit schedule will vary slightly between the groups to allow for those in the Treatment group to be implanted after the randomization visit. After the 1-year visit, patients in the Control group may elect to be implanted. The study schema is provided in Figure 3.

Figure 3: Study Schema

Total study duration is anticipated to be approximately 4 years from first enrollment to the last 2year visit.

### 3.1. Endpoints

### 3.1.1. Primary Efficacy Endpoint

#### 3.1.1.1. ODI

Oswestry Disability Index (ODI) is a disease specific assessment of the disabling effects of back pain. The ODI covers 1 item on pain and 9 items on activities of daily living (personal care, lifting, walking, sitting, standing, sleeping, sex life, social life, and traveling). ODI is reported as a score from 0 to 100.

The relevance of changes in ODI has been explored by many authors, and discussions abound on Minimal Clinical Important Difference (MCID), Minimally Important Change (MIC) and the like. Fairbank, et al., suggest a minimally important change is 15 points.

#### Hypothesis Test

The Primary endpoint is a comparison between the Treatment group and Control group of average change in ODI at 1 year compared to baseline.

The ODI efficacy endpoint will be tested under the following hypotheses:

 $\begin{array}{l} H_0: \ \mu ODI_T \ \text{-} \ \mu ODI_C \geq 0 \\ H_A: \ \mu ODI_T \ \text{-} \ \mu ODI_C < 0 \end{array}$ 

Where  $\mu$ ODIT is the mean change in ODI in the Treatment group and  $\mu$ ODIC is the mean change in ODI in the Control group at the 1-year visit. These hypotheses will be tested using the 1-year treatment effects contrast obtained from a mixed model for repeated measures (MMRM). The two-sided p-value for the equality null hypothesis will be reported as well as the two-sided adjusted 95% confidence interval for the difference in mean changes. Superiority will only be claimed if p<0.05 and the mean change is more negative (greater improvement) for the Treatment group compared to the Control group. This is equivalent to specifying a one-sided test at  $\alpha$ =0.025.

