#### **Inclusion Criteria**

1. Indicated for the ReActiv8 System

- Age ≥21 years
- Evidence of lumbar multifidus muscle dysfunction
- Intractable Chronic Low Back Pain that has persisted >6 months prior to enrollment, resulting in pain most of the days in the 12 months prior to enrollment
- Failed therapy including pain medications and physical therapy
- Not a candidate for spine surgery
- 2. Low Back Pain NRS of ≥6 and ≤9
- 3. Oswestry Disability Index score ≥30 and ≤60
- 4. Willing and capable of giving Informed Consent
- 5. Able to comply with this protocol
- 6. On Optimal Medical Management per the Investigator

Eligibility Criteria

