#### **Exclusion Criteria**

- 1. Contraindicated for the ReActiv8 System
  - Unable to operate the ReActiv8 System
  - Unsuitable for ReActiv8 implant surgery
- 2. BMI > 35
- 3. Back Pain characteristics:
  - Any surgical correction procedure for scoliosis at any time, or a current clinical diagnosis of moderate to severe scoliosis (Cobb angle ≥25°)
  - b. An independent MRI assessment identifying a pathology that is likely the cause of the CLBP and is amenable to surgery
- 4. Leg pain described as being worse than back pain, or radiculopathy (neuropathic pain) below the knee
- 5. Surgical or other procedures exclusions:
  - a. Any previous back surgery (e.g., laminectomy, discectomy, spinal fusion) at or below segmental level T8
  - b. Any previous thoracic or lumbar sympathectomy
  - c. Any lumbar rhizotomies within the past 12 months
  - d. Any lumbar nerve blocks within the past 30 days
  - e. Any previous or existing neuromodulation devices (e.g., drug pump, spinal cord stimulation, and/or peripheral nerve stimulation)
- 6. Other clinical conditions:
  - a. Pregnant or planning to be pregnant in the next 12 months
  - b. Any condition unrelated to CLBP such as muscle wasting, muscle atrophy, or progressive neurological disease which, in the opinion of the Investigator, could limit physical movement or compliance with the protocol, or interfere with the assessment of efficacy
  - c. Evidence of an active disruptive psychological or psychiatric disorder or other known condition significant enough to impact perception of pain, compliance with intervention and/or ability to evaluate treatment outcome (e.g., active depression, bipolar disease, Alzheimer's disease) as determined by the Investigator in consultation with a psychologist or psychiatrist as appropriate
  - d. An opioid addiction or drug-seeking behavior, as determined by the Investigator
  - e. Any active malignant disease
  - f. Any active infection in the vicinity of the implant site or any systemic infection
  - g. Poorly controlled diabetes (Type I or Type II) determined by HbA1c >8
- 7. General exclusions:
  - a. Current smoker
  - b. Current or planned participation in any other clinical trial during the study
  - c. A condition currently requiring or likely to require use of MRI or diathermy
  - d. Life expectancy less than one year

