### 3.1.2. Secondary Efficacy Endpoints

The same MMRM will be applied to NRS and EQ-5D. To control type 1 error, the p-values for superiority at 1 year will only be interpreted as inferential if the superiority for improvements in Year 1 ODI is demonstrated at 2-sided type 1 error rate of  $\alpha$ =0.05 (with hypothesized directionality). The Hochberg method (Hochberg 1988) will be used to control type 1 error among these two secondary endpoints.

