## 5.1. Informed Consent, Baseline Data, Inclusion Decision

The process for obtaining informed consent shall comply with the Declaration of Helsinki, Good Clinical Practice (GCP) and IRB requirements. Patients will be provided with the Informed Consent Form which advises that data will be collected for evaluation of eligibility for inclusion in the study. If the patient agrees to inclusion for data collection, the Informed Consent will be signed and recorded in the patient's records. The patient will then be assigned a unique study identifier. *Data to be collected:* 

- Screening data as required by the enrollment criteria
- Treatment Plan Worksheet per the RESTORE Treatment Guidelines document (980016)
- Medical History (including Physical Exam)
  - Baseline demographics
  - Comorbid conditions
  - $\circ~$  Characteristics of the patient's LBP such as diagnosis, duration, and number of episodes of LBP
- Depression Anxiety Stress Scale (DASS21)
- ODI
- LBP NRS
- EQ-5D
- Leg pain description and NRS
- Work status evaluation
- Healthcare utilization
- Pain treatments
- Download activity monitoring data (if applicable)

Activities to be performed:

- Answer any questions the patient may have and confirm willingness to proceed if the baseline criteria are verified
- Verify that the enrollment criteria are satisfied
- An MRI of the lumbar region of the low back will be performed or ordered if there are no MRI images from more recently than 1 year prior to enrollment. If an MRI is being performed for the purposes of this study, please follow the recommended settings (Appendix 1).
- MRI images will be reviewed to assess conditions that may be a possible cause of low back pain and to rule out possible surgical candidates by institutional guidelines
- Multifidus dysfunction assessment (e.g., Prone Instability Test, Lift test)
- Pregnancy test in women of child-bearing potential
- Assessment by the Investigator of the patient's suitability for ReActiv8 implant

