### 5.7. Mixed Model for Repeated Measures

These hypotheses will be tested using the 1 Year contrast estimated from a mixed model for repeated measures (MMRM) (Verbeke and Molenberghs 2000). The MMRM will include baseline endpoint value (ODI, NRS or EQ-5D), treatment group, visit, and visit by treatment group interaction. Changes from baseline to Months 1.5, 3, and 6, as well as from baseline to 1 Year are included in the MMRM as a function of the fixed effects. A random site effect will be included to account for the randomization within site. A random site effect is appropriate as we wish to generalize to patients from any site and specifically from sites included in this study. Patients lost-to-follow-up due to reasons related to lack of effectiveness or subsequent to a related AE will utilize baseline observation carried forward imputation of missing values; otherwise, missing values are implicitly imputed while estimating the parameters of the MMRM. MMRM produces unbiased estimates when there is missing follow-up when missing-at-random (MAR) assumption is true (Rubin 1976). The MAR assumption is that the likelihood of missing is statistically independent of the distribution of the unobserved missing outcome conditional on observed data and is most reasonable for missingness not associated with lack of efficacy.

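### The primary and secondary MMRMs adjust only for own baseline and site, although baseline DASS21, LBP NRS and EQ-5D are collected and could add modest precision if prespecified

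*Protocol*

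**What the plan says.** Protocol 3.1.1.1 names the method for ODI but not its covariates: "These hypotheses will be tested using the 1-year treatment effects contrast obtained from a mixed model for repeated measures (MMRM". Protocol 3.1.2 extends it to the secondary endpoints: "The same MMRM will be applied to NRS and EQ-5D".

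The covariates are in SAP 5.7: "The MMRM will include baseline endpoint value (ODI, NRS or EQ-5D), treatment group, visit, and visit by treatment group interaction". The same section adds: "A random site effect will be included to account for the randomization within site". Site is the only stratification factor, so the design is respected. No other patient-level baseline variable enters the three confirmatory models.

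Protocol 5.1 lists the "Depression Anxiety Stress Scale" (DASS21) among the baseline data, together with LBP NRS and EQ-5D, and Tables 4 and 5 tick all three at baseline for both groups. No eligibility criterion uses a DASS21 score. Apart from the data collection sections, DASS21 appears in the protocol only in the acronym list. The SAP does not mention it in the model (5.7), the baseline summary (5.3), or the subgroup and predictor lists (5.11). The 5.3 list and the main 5.11 lists are open-ended, so later use is allowed but not prespecified. SAP 4.4 lets other baseline factors be examined only if the site-by-treatment interaction gives p < 0.15.

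**The concern.** The protocol itself gives a reason to expect psychological state to be prognostic. Exclusion 6c bars patients with "Evidence of an active disruptive psychological or psychiatric disorder or other known condition significant enough to impact perception of pain", and goes on to mention the ability to judge treatment outcome. The primary and both secondary endpoints are patient-reported. Even so, the one psychological measure taken from every patient has no stated analytic use. Baseline NRS and EQ-5D, which SAP 5.11 already treats as relevant to the ODI effect, stay out of the ODI model.

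Two things are at stake. A prognostic baseline covariate that is left out leaves its variance in the residual, so the interval is wider than the collected data require. And if the arms happen to differ on such a factor, the primary estimate is not adjusted for it. Readers will ask about such a difference, and an adjustment chosen after the imbalance is seen carries less weight than one written down beforehand.

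**Working it through.** **1. The plan's own figure.** Inputs from Protocol 3.1.1.2 and SAP 3.2: difference 18.2 − 12.2 = 6.0; SD 15; two-sided 5%; power 80%; unadjusted t-test.

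- Normal approximation: n per arm = 2(1.960 + 0.842)² / (6/15)² = 98.1, rounded up to 99, so 198 in total.
- t-test: 99.08 per arm, rounded up to 100, so 200 in total.
- The stated 204 (102 per arm) is within 3% of both. Its t-test power is 81.1%.

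**2. Starting point for any gain.** The planned MMRM already adjusts for own baseline, so 81.1% is not the baseline for comparison. ASSUMPTION: own-baseline adjustment removes about 10% of the variance, close to a baseline-to-change correlation of 0.3 (0.3² = 9%). Then SD = 15√0.90 = 14.23, SE = 14.23 × √(2/102) = 1.99, and t-test power at 102 per arm is 85.0%. The t-test stands in for the 1-year contrast and ignores any gain from intermediate visits.

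**3. Adding DASS21 and the other endpoints' baselines.** ASSUMPTION: together they explain a fraction R² of the remaining variance. SD = 14.23 × √(1 − R²); equivalent extra patients = 204/(1 − R²) − 204.

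| Joint R² | SD | SE | Power | Equivalent extra patients |
|---|---|---|---|---|
| 0 | 14.23 | 1.99 | 85.0% | 0 |
| 2% | 14.09 | 1.97 | 85.7% | 4 |
| 10% | 13.50 | 1.89 | 88.5% | 23 |

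The SE falls by 1 − √0.98 = 1% to 1 − √0.90 = 5%.

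**4. Realized imbalance.** The standard error of a standardized between-arm difference is √(2/102) = 0.14 SD.

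- A one-SE imbalance in the joint prognostic score shifts the ODI difference by 0.14 × √R² × 14.23, which is 0.28 points at R² = 2% and 0.63 at 10%.
- For one covariate, if the joint R² splits equally over three independent covariates, the shift is 0.14 × √(R²/3) × 14.23, which is 0.16 to 0.36 points, or about 3% to 6% of the assumed 6-point effect.

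This variation is already part of the SE of 1.99.

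**The case against.** The strongest reply is that nothing here is an error. SAP 5.7 prespecifies a standard MMRM that includes the stratification factor. The sample size counts no covariate gain, and the plan itself calls that conservative. No document gives a correlation between DASS21 and any endpoint. Exclusion 6c may also narrow the DASS21 range, so the gain could be close to nothing. All of this stands.

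A late change to the primary model has its own risk. Rev D of the SAP is dated January 2024, for a study whose protocol was first released in March 2021. SAP 4.1 allows tables to be reviewed before final data lock. The documents do not say whether arm-level outcomes had been seen, so the change needs documented timing. A missing covariate value would also drop a patient from the model unless a rule is given. Both points shape the fix.

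A reader might infer more than the documents support:

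- **That the trial is underpowered.** It is not on its own inputs: 204 gives 81.1% before any adjustment.
- **That chance imbalance biases the result, more so in an open-label trial.** Randomization makes it zero on average, the standard error already includes it, and open-label treatment cannot change a covariate measured before randomization. There is no type I error inflation.
- **That the eligibility window ("Oswestry Disability Index score ≥30 and ≤60") wastes precision which other covariates could recover.** Take an assumed screening ODI of N(42, 14), 1-year SD 14 and correlation 0.5. The window cuts baseline SD to about 8.0 and own-baseline R² from 25% to 16/(16 + 147) = 9.8%. But residual SD is 14√0.75 = 12.1 with and without the window, and it is the residual SD that sets the standard error.

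**Conclusion.** The point holds as a low-cost improvement to a valid plan. The three confirmatory models use one patient-level baseline covariate each, while three further prerandomization measurements per model (DASS21 and the two other endpoints' baselines) are available, and DASS21 has no prespecified use at all.

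The likely benefit is modest: power from about 85.0% to between 85.7% and 88.5%, or about 4 to 23 patients' worth of information on 204. This rests on two assumptions that the documents cannot confirm: that own baseline removes about 10% of variance, and that the added covariates jointly explain 2% to 10% of the rest. If they explain nothing, there is no gain. The second benefit is a prespecified answer to a realized imbalance, which would typically be worth a few tenths of an ODI point. Open-ended lists in SAP 5.3 and 5.11 do not provide that, because they commit to nothing for DASS21, and subgroup analyses by NRS and EQ-5D do not adjust the primary contrast.

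**What to change.** Amend SAP 5.7 before any outcome data are reviewed by arm:

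- Prespecify baseline DASS21 total, LBP NRS and EQ-5D index as fixed covariates in all three MMRMs, with baseline ODI added where it is not the endpoint's own baseline.
- State a simple rule for missing baseline covariates, for example imputing the overall mean without regard to arm, so that no patient is dropped.
- Keep the current model as a supporting analysis.
- Record the date of the change and that arm-level outcomes had not been seen.

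If arm-level data have already been seen, keep the current model as primary and make the adjusted model the supporting analysis.

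The cost is about 3 model degrees of freedom out of about 200 and one SAP amendment. No new data are needed.

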#### 3.1.1.2. Sample Size Rationale

The sample size for the study is determined under the following assumptions for the primary efficacy endpoint, which are based on a prior study of ReActiv8, and approximately the MMRM test by its corresponding unadjusted t-test. All else being equal, this is a conservative estimate of power since control for baseline and inclusion of intermediate time points is not accounted for.

- Minimum power of 80%
- Type I error of 5%
- Assumed mean change in Treatment group: 18.2
- Assumed mean change in Control group: 12.2
- Pooled Standard Deviation: 15

Under the above assumptions, a minimum of 204 evaluable patients is required in order to demonstrate superiority of the ReActiv8 treatment. To account for attrition, approximately 230 patients will be enrolled and randomized.

### 3.1.2. Secondary Efficacy Endpoints

The same MMRM will be applied to NRS and EQ-5D. To control type 1 error, the p-values for superiority at 1 year will only be interpreted as inferential if the superiority for improvements in Year 1 ODI is demonstrated at 2-sided type 1 error rate of  $\alpha$ =0.05 (with hypothesized directionality). The Hochberg method (Hochberg 1988) will be used to control type 1 error among these two secondary endpoints.

#### 3.1.2.1. Low Back Pain NRS

Average Low Back Pain will be measured using the 11-point Numerical Rating Scale for Low Back Pain (Figure 4), as recommended by IMMPACT. Specifically, the NRS scale for "average low back pain in the last 24 hours" will be used.

Figure 4: 11-Point Numerical Rating Scale for Low Back Pain

The endpoint will compare change from baseline in NRS between Treatment and Control groups at the 1-year visit.

